### **10.8 Power for analysis of critical secondary variables**

Not applicable

## 10.9 Subgroup analyses

Since the study population will consist of subjects treated with Omnitrope® 5 mg/ml powder for the first twelve months and with Omnitrope® 5 mg/1.5 ml solution for injection thereafter as well as of subjects treated continuously with Omnitrope® 5 mg/1.5 ml solution for injection, a corresponding subgroup analysis will be performed. The main focus of such subgroup analysis will be on the comparison of the safety profiles during the first twelve months of treatment as well as on the effects on the growth related parameters for the first twelve months of treatment and also for the whole treatment period.

Further subgroup analysis will be done for an overweight population with **international cut-off points for BMI for overweight by sex and age as defined by the percentile that passes through BMI of 25 at age 18**.

All comparisons will be performed descriptively using adequate frequency tables and descriptive statistics. Details of the analyses will be laid down in the statistical analysis plans for the respective (interim) analyses.

## 11 Discussion and rationale for study design features

This study has been designed in accordance with the post-approval pharmacovigilance plan to extend the safety database of Omnitrope® and to address the EMEA's request:

- to investigate the diabetogenic potential of Omnitrope® in short children born SGA, and
- to further investigate the immunogenicity of Omnitrope® in short children born SGA.

More specifically, the primary objective of this study is:

- to monitor the development of diabetes during Omnitrope® treatment.

The secondary objectives of this study are:

- to monitor the development of anti-hGH antibodies during Omnitrope® treatment,
- to evaluate the safety (incidence and occurrence of adverse events) of Omnitrope® treatment in short children born SGA, and
- to evaluate the efficacy (with respect to changes in height parameters, serum IGF-I and IGFBP-3 levels) of Omnitrope® treatment in short children born SGA.

All included subjects will receive Omnitrope® 0.035 mg/kg/day as per recommended dose for short stature secondary to SGA. Dose adjustments will be allowed during therapy consistent with label recommendations. Omnitrope® treatment will continue until final height is reached but will be discontinued earlier if there is inadequate response to treatment (e.g., height velocity standard deviation score (HVSDS) remains below +1 in the first year).

To address concerns regarding the risk of developing diabetes mellitus in GH-treated short children born SGA, specific parameters such as fasting plasma glucose and insulin levels will be measured at pre-defined time points throughout treatment with Omnitrope®.

Subjects will be monitored for safety throughout treatment. Height, height SDS, HV and HVSDS will be determined until final height is reached.

## **12 Procedures and instructions: Administrative procedures**

### **12.1 Changes to the protocol**

Any change or addition to this protocol requires a written protocol amendment that must be approved by Sandoz, the Coordinating Investigator as well as the Principal Investigator(s) before implementation. Amendments significantly affecting the safety of subjects, the scope of the investigation or the scientific quality of the study, require additional approval by the IRB/IEC of all centers, and, in some countries, by the regulatory authority. A copy of the written approval of the IRB/IEC and the regulatory authority, where applicable, must be given to the study monitor.

### **12.2 Ethics and Good Clinical Practice**

This study must be carried out in compliance with the protocol and the principles of Good Clinical Practice:

ICH Harmonized Tripartite Guidelines for Good Clinical Practice 1996.  
Directive 91/507/EEC, The Rules Governing Medicinal Products in the European Community.

**Directive 2001/20/EC, EU Clinical Trials Directive**

**Directive 2005/28/EC, EU GCP Directive**

**91/507/EEC, The Rules Governing Medicinal Products in the European Community**

**MEDDEV 2.12-1 rev 5, Guidelines on a Medical Devices Vigilance System**

US 21 Code of Federal Regulations dealing with clinical studies (including parts 50 and 56 concerning informed consent and IRB regulations).

Declaration of Helsinki and amendments, concerning medical research in humans (Recommendations Guiding Physicians in Biomedical Research Involving Human Subjects).

The investigator agrees when signing the protocol to adhere to the instructions and procedures described in it and thereby to adhere to the principles of Good Clinical Practice that it conforms to.

#### **12.2.1 Institutional Review Board/ Independent Ethics Committee**

Before implementing this study, the protocol, the investigator brochure, the curriculum vitae of the investigators, the proposed informed consent form and other information to subjects, will be submitted to a properly constituted Institutional Review Board/Independent Ethics Committee (IRB/IEC) according to national law. The study will only be performed at a study site if a full approval of the protocol has been obtained by the IRB/IEC.

#### **12.2.2 Informed consent**

The investigator must explain to each patient (and/ or legally authorized representative) the nature of the study, its purpose, the procedures involved, the expected duration, the potential risks and benefits involved and any discomfort it may entail. Each subject must be informed that participation in the study is voluntary and that he/she may withdraw from the study at any

time and that withdrawal of consent will not affect his/her subsequent medical treatment or relationship with the treating physician.

To cover adolescence of the patients with adequate patient information documents, three patient information documents, one for children between 4 and 6 years of age, one for children between 7 and 12 years of age, and one for children  $\geq$  13 years of age are used within this clinical trial. Children who can read and write should sign the informed consent on the basis of the patient information document according to their relevant age group. At all events written informed consent has to be obtained from the patients' parents or legal guardian.

These informed consent(s) should be given by means of a standard written statement, written in non-technical language. The subject/parents or legal guardian should read and consider the statement before signing and dating it, and should be given a copy of the signed document.

If the subject cannot read or sign the documents, oral presentation may be made and ~~or~~ signature given by the subject's legally appointed representative, if witnessed by a person not involved in the study, mentioning that the patient could not read or sign the documents. No patient can enter the study before his/her informed consent has been obtained.

Female patients of child bearing potential must be informed that taking the study drug may involve unknown risks to the fetus if pregnancy were to occur during the study and agree that in order to participate in the study they must adhere to the contraception requirement for the duration of the study. If there is any question that the subject will not reliably comply, they must discontinue the study.

The informed consent form is considered to be part of the protocol, and must be submitted by the investigator with it for IRB/IEC approval.

### **12.2.3 Declaration of Helsinki**

The investigator must conduct the trial in accordance with the principles of the Declaration of Helsinki. The Declaration of Helsinki (Document 17.C) is an official policy document of the World Medical Association, the global representative body for physicians. It was first adopted in 1964 (Helsinki, Finland) and revised in 1975 (Tokyo, Japan), 1983 (Venice, Italy), 1989 (Hong Kong), 1996 (Somerset-West, South Africa) and 2000 (Edinburgh, Scotland). Note of clarification on Paragraph 29 added by the WMA General Assembly, Washington 2002. Note of Clarification on Paragraph 30 added by the WMA General Assembly, Tokyo 2004.

## Appendices

### Tanner Breast Stages

Stage 1	Pre-adolescent; elevation of papilla only.
Stage 2	Breast bud stage; elevation of breast and papilla as a small mound, enlargement of areola diameter.
Stage 3	Further enlargement of breast and areola, with no separation of their contours.
Stage 4	Projection of areola and papilla to form a secondary mound above the level of the breast.
Stage 5	Mature stage; projection of papilla only, due to recession of the areola to the general contour of the breast.

Source: Marshall WA, Tanner JM: Variations in Pattern of Pubertal Changes in girls.  
Arch Dis Childh 1969; 44: 291-303

### Handling of elevated blood glucose levels and OGTT

Fasting blood glucose levels	OGTT	Patient outcome
impaired	impaired	Ongoing
overt	impaired	Ongoing
overt	overt	Discontinuation

As the OGTT is more sensitive than fasting blood glucose assessment, the final decision with regards to discontinuation will be eventually based on the result of the OGTT.

In case of the unlikely situation that fasting blood glucose levels = normal/impaired and OGTT=overt, patient outcome = discontinuation.

Overt levels are defined as:

- Fasting blood glucose  $\geq 126$  mg/dl or  $\geq 7.0$  mmol/l
- OGTT  $\geq 200$  mg/dl or  $\geq 11.1$  mmol/l after 120 minutes

## Recommended Dosage of Omnitrope®

5 mg / 1.5 ml cartridge		10 mg / 1.5 ml cartridge	
Weight in kg	Dose dialed in mg	Weight in kg	Dose dialed in mg
5.0 – 6.4	0.20	45.0 – 46.4	1.60
6.5 – 7.8	0.25	46.5 – 47.8	1.65
7.9 – 9.2	0.30	47.9 – 49.2	1.70
9.3 – 10.7	0.35	49.3 – 50.7	1.75
10.8 – 12.1	0.40	50.8 – 52.1	1.80
12.2 – 13.5	0.45	52.2 – 53.5	1.85
13.6 – 14.9	0.50	53.6 – 54.9	1.90
15.0 – 16.4	0.55	55.0 – 56.4	1.95
16.5 – 17.8	0.60	56.5 – 57.8	2.00
17.9 – 19.2	0.65	57.9 – 59.2	2.05
19.3 – 20.7	0.70	59.3 – 60.7	2.10
20.8 – 22.1	0.75	60.8 – 62.1	2.15
22.2 – 23.5	0.80	62.2 – 63.5	2.20
23.6 – 24.9	0.85	63.6 – 64.9	2.25
25.0 – 26.4	0.90	65.0 – 66.4	2.30
26.5 – 27.8	0.95	66.5 – 67.8	2.35
27.9 – 29.2	1.00	67.9 – 69.3	2.40
29.3 – 30.7	1.05	69.4 – 70.7	2.45
30.8 – 32.1	1.10	70.8 – 72.1	2.50
32.2 – 33.5	1.15	72.2 – 73.5	2.55
33.6 – 34.9	1.20	73.6 – 75.0	2.60
35.0 – 36.4	1.25	75.1 – 76.4	2.65
36.5 – 37.8	1.30	76.5 – 77.8	2.70
37.9 – 39.2	1.35	77.9 – 79.3	2.75
39.3 – 40.7	1.40	79.4 – 80.7	2.80
40.8 – 42.1	1.45	80.8 – 82.1	2.85
42.2 – 43.5	1.50	82.2 – 83.5	2.90
43.6 – 44.9	1.55	83.6 – 85.0	2.95

**Document History – Changes compared to previous version of the SAP.**

Date	Version	Title	Purpose of the SAP / Main Changes
25-Nov-2009	1.0	Statistical Analysis Plan for Protocol Number: EP00-401	Initial version
27-Jul-2011	1.0	Statistical Analysis Plan for Interim Analysis	Specific SAP version used for the 1 year interim analysis Outputs limited to data collected during the first year of treatment
19-Jan-2012	1.0	Further statistical Methods for Interim Analysis	Document specifying further programming details for 1 year interim analysis
13-Feb-2012	1.0	Statistical Analysis Plan for Interim Analysis – SAP Amendment	Amendment to specific SAP version used for the 1 year interim analysis
10-Oct-2013	2.1	Statistical Analysis Plan for 2 Years Interim Analysis	Specific SAP version used for the 2 years interim analysis Outputs limited to data collected during the first two years of treatment
18-Apr-2017	1.0	Statistical Analysis Plan – Interim Analysis 2017	Specific SAP version prepared for a third interim analysis planned for 2017. All data available at database cut-off to be analysed. This interim analysis was not performed.
11-May-2017	2.0	Statistical Analysis Plan – Interim Analysis 2017 (Note: The interim analysis 2017 was not performed.)	Updated version of the specific SAP version prepared for a third interim analysis planned for 2017 based on discussions during the DRM meeting. This interim analysis was not performed.
31-May-2021	4.0	Statistical Analysis Plan	SAP version for the final analysis including all data available. Main changes: Removal of per protocol set according to Protocol Amendment 04 dated 24-Aug-2017 Updated Type 2 diabetes mellitus definition to 2016 revised WHO criteria which includes HbA 1c . Definitions for IGT and IFG added.
26-Apr-2022	5.0	Statistical Analysis Plan	SAP version for the final analysis including all data available. Main changes: Subgroup analysis of an overweight population added. Additional tables and figures added.

## List of abbreviations

ADA	Anti-drug antibodies
AE	Adverse event
█	█
CA	Chronological age
CRF	Case report form
FAS	Full analysis set
FPG	Fasting plasma glucose
HA	Height age
HbA 1c	Glycated hemoglobin test
HCP	Host Cell Protein
HOMA	Homeostasis model assessment
HV	Height velocity
HV SDS	Height velocity standard deviation score
IFG	Impaired fasting glucose
IGT	Impaired glucose tolerance
OGTT	Oral glucose tolerance test
Q1	First quartile
Q3	Third quartile
QUICKI	Quantitative insulin sensitivity check index
rhGH	Recombinant human growth hormone
SAE	Serious adverse event
SAF	Safety set
SD	Standard deviation
SGA	Small for gestational age

## 1 Introduction

This study is performed as part of the Marketing Authorization Holder's post-authorization Risk Management Plan in order to investigate the long-term safety, in particular the diabetogenic potential and immunogenicity of Omnitrope treatment in short children born small for gestational age (SGA).

This study is designed as an open phase IV, prospective, non-comparative, multicenter trial. Omnitrope treatment will continue until final height is reached. Treatment should be discontinued after the first year of treatment if the height velocity standard deviation score (HV SDS) is below +1. Treatment should be discontinued if height velocity is below 2 cm/year

## 2 Statistical and analytical plans

Data will be analyzed by [REDACTED] according to this statistical analysis plan.

### 2.1 Study documents and general considerations

This document describes the procedures and conventions to be used for the final analysis of all patients who were included into study EP00-401 and is based on study protocol V6.0, dated 07-Feb-2020, incorporating amendment no. 05.

Raw data listings, summary tables, graphs and statistical tests will be generated by means of the program SAS 9.4 and SAS/STAT Version 14.3.

The following descriptive statistical parameters will be shown in summary tables

- Continuous variables: n (valid cases), n (missing data), mean, standard deviation (SD), min, 1st quartile (Q1), median, 3rd quartile (Q3), max
- Categorical variables: Count and percentage of category. Percentages are routinely based on the total category count excluding the missing category if not otherwise mentioned. Percentages showing a rate relative to the total number of patients in this group are given in special tables (e.g. Adverse Event (AE) tables). Footnotes will specify the percent basis.

For continuous variables, if not otherwise specified, mean, median and standard deviation values will be reported to one decimal place greater than the data were collected. Minimum and maximum values will be reported with the same precision, as they were collected.

Generally, percentages will be displayed in the format xx.d, i.e. one decimal place will be shown; if the calculated percentage is 100, no decimal is required (i.e. 100% and not 100.0%). If the count is zero no percentage needs to be shown.

### 2.2 Study objectives

The primary objective of this study is to evaluate the long-term effect of growth hormone treatment on the development of diabetes in short children born SGA during the treatment.

The secondary objectives of this study are:

- to report the incidence of anti-recombinant human growth hormone (rhGH) antibodies during Omnitrope treatment
- to evaluate the efficacy (with respect to changes in height parameters) of Omnitrope treatment in short children born SGA
- to evaluate IGF-1 and IGFBP-3 levels during treatment
- to evaluate incidence and severity of adverse events

## 2.3 Endpoints

### 2.3.1 Primary endpoint

The development of diabetes is the primary endpoint of the study and is evaluated on the basis of the carbohydrate metabolism (fasting plasma glucose (FPG), oral glucose tolerance test (OGTT)) and HbA1C.

### 2.3.2 Secondary endpoints

The development of anti-rhGH antibodies is a secondary endpoint.

The efficacy endpoints of this study are the height and the standardized height (SDS), the height velocity (HV) and the HV SDS assessed at screening, every 3 months during the first two years of GH treatment and annually thereafter until final height is reached (end of treatment).

Additionally efficacy endpoints of this study are the development of the hGH-induced serum parameters IGF-1 and IGFBP-3 assessed by a central laboratory at screening, after 3, 6, 9, 12 months and then biannually during treatment.

Additional criteria for assessing safety will consist of monitoring and recording all (serious) adverse events, vital signs and body weight, physical condition, hematology, blood chemistry, thyroid function tests, lipids and urinalysis. Fundoscopy will be performed if intracranial hypertension is suspected.

## 2.4 Statistical methods planned in the protocol

Analyses planned are described in section 10 of the protocol.

Safety and efficacy endpoints will be summarized descriptively. For all efficacy endpoints mean difference between the baseline visit and all later visits and respective 95% confidence will be provided.

## 2.5 Determination of sample size

There was no formal sample size calculation for this study which is intended to exploratorily investigate the long-term effect of the treatment with respect to the development of diabetes. No such incidences are currently available to allow for a rigorous sample size estimation. Results obtained in this study will be compared to data published in the literature.

[REDACTED]  
Patients dropping out before completing 1 year of treatment will be replaced.

## 2.6 Definitions of analysis sets

The **safety analysis set** (SAF) comprises all patients who have received at least one dose of study medication and had at least one post-baseline safety assessment. All safety analyses will be based for the SAF.

The **full analysis set** (FAS) follows the intent-to-treat principle and consists of all patients who received at least one dose of study medication.. All baseline and efficacy analyses will be summarized for the FAS.

## 2.7 Subgroup analyses

Since the study population consists of patients treated with Omnitrope 5 mg/ml powder for the first twelve months and with Omnitrope 5 mg/1.5 ml solution for injection thereafter as well as of patients treated continuously with Omnitrope 5 mg/1.5 ml mg/ml solution for injection, a corresponding subgroup analysis will be performed.

Moreover, a subgroup analysis will also be done for an overweight population with international cut-off points for BMI for overweight by sex and age as defined by the percentile that passes through BMI of 25 at age 18.

Further subgroup investigations concerning efficacy endpoints will be carried out with regard to sex, completers and total.

## 3 Changes to planned analyses

The assessment of laboratory findings related to diabetes mellitus is no longer based on WHO definition of 2006, but on the version published in 2016.

The protocol planned to analyze treatment compliance based on the percentage of medication used compared to the amount prescribed for each visit and the frequency of non-compliant patients (daily dose range 80% or >120%). This approach was changed currently the number of non-compliant patients will be assessed based on the investigator's assessment that is collected on dose change page in the CRF.

Analysis for anti-HCP was added.

## 4 Statistical analyses

### 4.1 General considerations

#### Baseline visit

In principal, Visit V01 (start) is regarded as baseline visit. For some patients only a screening visit, but no baseline visit was performed. For these patients screening visit will be used as baseline visits.

#### Alignment of final visits

A final visit should be performed for all patients terminating study drug. These visits will be analyzed together with the regularly performed study visits. A final visit will be assigned to the appropriate study visit as follows:

In a first step the respective limit between two visit used for assignment, will be assessed as follows: limit = (Day on which VX [= Visit X] should have been performed - Day on which VX-1 should have been performed)/2. The respective limit was rounded if necessary. Days on which a visit should have been performed according to protocol will be assessed as follows (excluding V0 and V1): Month given in the protocol \*(365.25/12) (i.e. V2 = Day 92, V3 = Day 183, V4 = 274 ...).

In a second step final visits performed between VX-1 and the limit (included) will be assigned to VX-1, final visits performed after the limit and prior to VX will be assigned to VX.

For example: A final visit performed between V3 and V4, will be assigned to V3, if performed at or before Day 229 (= (Day 274 + Day 183)/2 = 228.5 => rounded to 229). If performed after Day 229 and at or before V4, the final visit will be assigned to V4.

If due to the assignment of final visits to regular visits two assessments are available for one visit, the assessment nearest to the day on which the visit had to be performed will be used.

If the final visit was performed on the same day as a regular visit, the regular visit will be used for analysis.

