In the same study ([Hokkon-Koelega et al 2004](#), [Sas et al 2001](#)), all 79 children underwent standard oral glucose tolerance tests at baseline, after 1 and 6 years of GH treatment and 6 months after discontinuation of GH therapy. Before GH therapy 8% of the children had impaired glucose tolerance (IGT) according to WHO criteria. IGT was found in 4% of children after 6 years of therapy and in 10% of children after stopping GH treatment. GH therapy induced considerably higher fasting and glucose-stimulated insulin levels, indicating insulin resistance. After discontinuation of GH therapy the mean serum glucose levels remained normal and the mean serum insulin levels decreased significantly, to normal age-matched reference values. HbA1C levels were always in the normal range and none of the children developed diabetes mellitus.

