### **6.5.9 Study drug discontinuation**

Treatment can be terminated at any time, at the discretion of the investigator or the Sponsor, or at the patient's request, in the event of an AE or due to treatment failure.

Study drug treatment has to be discontinued in the following cases during treatment period:

- Occurrence of overt diabetes mellitus; defined as fasting blood glucose  $\geq 126$  mg/dl or  $\geq 7.0$  mmol/l and abnormal findings in OGTT defined by  $\geq 200$  mg/dl or  $\geq 11.1$  mmol/l after 120 minutes. For further instruction see appendix
- Requirement of an increase of the recommended dose to obtain increased growth velocity
- Renal transplantation
- Diagnosis of benign intracranial hypertension
- Malignancy
- Pregnancy
- Withdrawal of informed consent
- Treatment failure

Treatment failure is defined as: Inadequate response to treatment, e.g. height velocity standard deviation score (HVSDS) below +1 in the first year.

Furthermore a standardized controlled procedure for the calculation of the treatment response (via "Treatment Response Control Fax") was implemented (see also 6.5.3 treatment duration) to ensure a unified flawless computation and to authorize treatment continuation, if applicable (managed by Data Management at Metronomia). In case the Investigator does not agree with the assessment by Data Management, Sandoz is informed and initiates the re-assessment of the treatment response data via an independent specialist reader.

Patients who are withdrawn from the study before completing at least one year of treatment with Omnitrope® will be replaced.

Study drug must be discontinued if the investigator concludes that continuation would result in significant safety risk for that patient and in the event of pregnancy.

Patients who discontinue study drug before completing the study should not be considered withdrawn from the study and should be scheduled for a final visit as soon as possible, at which time all of the assessments for the final visit will be performed.

A Study Drug Discontinuation form should be completed, giving the date and reason for stopping the study drug. All patients who discontinue study drug, including those who refuse to return for a final visit, will be contacted for safety evaluations during the 4 weeks following the last dose of the study drug.

Patients who discontinued this study for any reason will not be able to re-enter the study.

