## 7 Visit Schedule and assessments

The Flow Chart (synopsis) lists assessments and indicates with an “X” the visits during which they are performed. Patients should be seen for all visits at the designated time-point or as close to it as possible. A time window for the visits of up to +/- three weeks will be allowed.

All data obtained from the assessments listed in the Flow-Chart and described in detail in the subsections below must be supported in the patient’s source documentation.

The study visit schedule consists of screening period for up to 8 weeks prior to the initiation of therapy followed by an open treatment period until final height is reached. The study plan timetable (please refer to the Flow Chart Treatment Period) indicates the number and timing of the planned visits. During these visits, the mentioned efficacy and safety parameters will be assessed. It is important to maintain the visit schedule during the treatment period as accurately as possible. If any individual visit date does not conform to the planned schedule, the subsequent visit should be realigned to maintain the schedule relative to the start of the treatment period.

The clinical and laboratory investigational plan per visit is summarized in the Flow Chart Treatment Period.

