### **4.4 Treatment regimen, compliance and exposure to drug**

The patient's exposure to study drug will be calculated from the date of first dose to the date of last study drug administration for patients that prematurely discontinued or completed the study, and presented in years as a decimal.

If date of last study drug administration is missing completely or only a year is given and the patient has discontinued or completed the study, then the date the patient discontinued or completed the study shall be used instead. If date of last study drug administration was given only partial (i.e. month and year given), the first date of the month will be assumed as last administration date. Study drug exposure in days will be converted to study drug in years as follows:

- Exposure (years) = Exposure (days)/365.25.

The patient's exposure to study drug will also be summarized by site for FAS.

The total daily dose administered per kg body weight will be summarized by visit to assess the appropriateness of the applied dose for FAS.

A summary table providing the number and percentage of patients with any study drug dose change documented by reason for dose change overall and by number of times the respective reason was documented per patient will be provided. As for some patients dose change records

were documented when the patient returned to the recommended dose, all records with a daily dose of 0.035 mg/kg will be excluded from the summary tables.

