#### **4.6.1.1 IGF-1 and IGFBP-3 serum levels**

Blood samples for the determination of IGF-1 and IGFBP-3 serum levels will be drawn at baseline, at 3, 6, 9, 12, 18, and 24 months, then every 6 months during treatment, and at the end of treatment. Serum levels as well as ratios of IGF-1 and IGFBP-3 will be assessed by a central laboratory.

Data regarding secondary efficacy parameters will be summarized by visit overall and stratified by sex and initially treatment. In summary tables by visit overall confidence limit for means will be provided. Time trends of means will be presented graphically for all patients only by sex. In addition, 95% confidence intervals will be calculated for the mean difference between the baseline visit and all later visits, respectively. Relative changes from baseline of IGF-1 and IGFBP-3 will be summarized by visit.

Shift tables for changes in the reference range classification will be provided for IGF-1 and IGFBP-3. Shift tables will be prepared for the two formulations separately. In these tables baseline data will be presented in rows and data from the visits at 6, 12, 18, and 24 months will be cross-tabulated in columns. The categories "low"(< lower limit of normal), "normal", "high" (>upper limit of normal) and "missing" will be used in the shift tables. Shifts between categories will be displayed using absolute counts.

IGF-1, IGFBP-3 and ratio will be expressed in SDS. SDS reflects the deviation of a measured value from the mean value of healthy children of the same sex and chronological age, expressed in units of the standard deviation of unexposed children of the same sex and chronological age.

Standardization of patients' IGF-1, IGFBP-3 and ratio will be performed according to Elmlinger (2004). SDS values will be assessed according to the following formulas:  $SDS = (X1 - X2) / ((X2 - X3) / 2)$  if  $X1 < X2$  and  $SDS = (X1 - X2) / ((X4 - X2) / 2)$  if  $X1 \geq X2$ , where X1 means the measured value, X2 the mean value for the relevant chronological age and sex, X3 the -2 SD value for the relevant chronological age and sex, and X4 the +2 SD value for the relevant chronological age and sex according to Elmlinger (2004).

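### Final visits are merged into calendar visits with no limit on days since last dose, so off-drug samples can enter the on-treatment IGF-1 and carbohydrate summaries

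*SAP*

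**What the plan says.** SAP 4.1 (Alignment of final visits) covers every patient who ends study drug: "These visits will be analyzed together with the regularly performed study visits". Assignment depends on the day of the visit: "final visits performed between VX-1 and the limit (included) will be assigned to VX-1", and later ones go to the next visit. If two assessments land in one slot, the one nearer the nominal day is used. No criterion refers to the last dose, either there or in SAP 4.6.1.1 (IGF-1, IGFBP-3) or 4.6.2.2 (carbohydrate metabolism).

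Protocol 6.5.9 says that patients who stop drug early "should be scheduled for a final visit as soon as possible", with no maximum gap. Protocol 7.1.12 repeats the carbohydrate and IGF tests at that visit. The general window is loose: "A time window for the visits of up to +/- three weeks will be allowed".

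Protocol 10.4.1 and 10.5.2 list end of treatment as a separate time point and promise descriptive statistics for each visit. SAP section 3 records three changes to the planned analyses, and this merge is not one of them. The last-dose date is already in use: SAP 4.4 measures exposure "to the date of last study drug administration".

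**The concern.** The by-visit tables will be read as values on treatment. A child who has stopped injecting and is sampled some weeks later contributes a value that may no longer reflect the drug. Protocol 1.2.4 reports from an earlier study that after growth hormone was stopped "the mean serum insulin levels decreased significantly, to normal age-matched reference values". SAP 2.3.2 describes IGF-1 and IGFBP-3 as induced by the hormone. Off-drug values would therefore tend to pull mean insulin and HOMA, and plausibly IGF-1, back towards baseline, and push QUICKI up. With one arm, no control group would reveal this.

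Early stopping is built into the design. Protocol 6.5.3 and 6.5.9 call for discontinuation after an inadequate first-year response, which puts some final visits in or near the V05 and V06 rows. At stake are the secondary objective on IGF-1 and IGFBP-3 during treatment and the descriptive carbohydrate summaries.

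**Working it through.** **1. The plan's own figure.** Nominal day = month x 365.25/12. Months 3, 6 and 9 give 91.31, 182.63 and 273.94; rounded up, these are the SAP's Days 92, 183 and 274. The worked example for V3 and V4 reads "Day 274 + Day 183)/2 = 228.5 => rounded to 229", and this midpoint reproduces. The formula as written, half the difference, gives (274 - 183)/2 = 45.5, so the written formula and the example need reconciling. The rest of this check uses the midpoint.

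**2. How far a final visit may lie from its slot.** Half the spacing is about 46 days when visits are 3 months apart (for example (366 - 274)/2 = 46) and about 91 days when they are 6 months apart (for example (1096 - 914)/2 = 91). The protocol window is 21 days. These are distances from the nominal day, not days off drug; the rule puts no bound on the latter.

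**3. Replacement of an on-drug value.** Illustration: V05 is done on Day 345, drug is then stopped, and the final visit is on Day 370. The V05/V06 limit is (366 + 457)/2 = 411.5, so Day 370 goes to V05. Distances from Day 366 are 366 - 345 = 21 and 370 - 366 = 4. The final-visit value is kept and the on-drug value drops out of the table.

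**4. Rows with no scheduled test.** In the protocol flow chart, glucose, insulin, HbA1c and OGTT are not scheduled at V02, V04, V06 to V08, V10, V12, V14 and so on. Final visits would supply essentially all routine carbohydrate values in those rows. IGF-1 differs: it is scheduled at the half-year visits from V10, and is unscheduled only at V06 and V08.

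**5. Size.** Let D be the on-drug mean change, f the off-drug share of a row, and r the fraction of D reversed by the time of sampling. Assume the same D in early stoppers and other patients. Then

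pooled mean change = (1 - f) x D + f x (1 - r) x D = (1 - f x r) x D.

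The documents give neither f nor r, so both are assumed:

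| f | attenuation at r = 0.25 | at r = 1 |
|---|---|---|
| 5% | 1.25% | 5% |
| 10% | 2.5% | 10% |
| 20% | 5% | 20% |
| 50% | 12.5% | 50% |

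If samples are taken at or near the last dose, r is close to 0 and so is the attenuation.

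**The case against.** The documents point towards short gaps. The final visit is the planned end-of-treatment assessment, unused drug is returned at it, its window is three weeks either way, and early stoppers are to come promptly. Completers should be sampled near their last dose. This stands: the exposure lies mainly with early discontinuers, and dilution is a possibility, not a demonstrated fact.

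The evidence for reversal is limited. The earlier study tested 6 months after stopping, so it says nothing about reversal within days or weeks, and the documents give no off-drug figure for HOMA or IGF-1. This also stands, and is why r is left as a range.

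SAP 4.6.1 presents efficacy analyses, including IGF-1, for completers as well as in total, which partly isolates the problem. It does not help the carbohydrate tables, which have no such split.

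A last-dose rule has weaknesses of its own. SAP 4.4 sets a last-dose date known only to the month to the first of that month, so a last dose on the 28th sampled on the 30th would appear 29 days old. It replaces a missing date with the discontinuation or completion date, which could hide a real gap. The fix has to handle both. Protocol 6.5.4 also permits interruptions of up to 3 weeks in continuing patients, and a final-visit flag will not catch those.

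A reader might infer three stronger things that the documents do not support:

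- **That the primary result is diluted.** Diabetes is counted if any criterion is met (SAP 4.6.2.2), and averaging cannot remove a positive finding.
- **That every off-drug value is reassuring.** The same earlier study found IGT in 4% after 6 years of therapy and in 10% after stopping.
- **That rows made up of final visits are wholly off drug.** A completer sampled at end of treatment is not off drug.

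**Conclusion.** The gap in the plan is real: final visits are pooled by study day with no last-dose limit, which departs from the protocol's separate end-of-treatment time point without being declared. It affects the by-visit and change-from-baseline summaries of IGF-1, IGFBP-3, fasting glucose, insulin, HOMA and QUICKI.

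Its size is unknown and may be negligible. The 5% to 20% range rests on an assumed 20% off-drug share and on reversal of a quarter to all of the effect. The sponsor can establish the share from dates already held, except where the last-dose date is imputed. No powered comparison is at risk, since the study is descriptive. The correction is worth making because it is cheap and makes the during-treatment summaries mean what they say.

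**What to change.** In SAP 4.1:

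- Derive days from last dose to each final-visit sample and report their distribution.
- In the by-visit and change-from-baseline tables for the parameters above, including the IGF-1/IGFBP-3 ratio and the SDS values, use final-visit values only within a pre-specified interval of the last dose (for example 7 days, with a sensitivity analysis at 21 days).
- Put later samples in a separate end-of-treatment row with median days off drug. Do the same for carbohydrate samples falling at visits where none is scheduled and, on the same logic, IGF samples at V06 and V08.
- Classify samples whose last-dose date is missing or partial, and so imputed under SAP 4.4, as gap unknown.
- Add a sensitivity summary without final visits.
- State that all samples, including any displaced by the nearest-day rule, stay in the diabetes, IGT and IFG counts.
- Reconcile the limit formula with its example.

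List the change in SAP section 3. The cost is SAP wording, a derived variable with a gap-unknown category, and a few extra table rows, with no new data. The downside is slightly smaller n in some late-visit rows.
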